10.3. Recruitment and Retention Practices

10.3.1. The 3E Approach

The CCC will work closely with the DCC to develop training and certification requirements during the UG3 phase that is aimed at successful recruitment and retention. We plan to use a trident approach to recruitment and retention training that is focused on education, empathy, and engagement, the 3E Approach, coined by the OSU Clinical Trials Management Organization (CTMO). In our experiences in leading multidisciplinary multi-site trials, we believe education is the most powerful tool in the recruitment and retention practices toolbox. Extensive training of research personnel will focus on equipping study coordinators and study nurses with sufficient knowledge of heart failure and sleep disordered breathing. Although we have chosen experienced sites that have performed well in either heart failure or sleep medicine research trials, we understand that each site may be organized in disease-specific groups and as a result, are most well versed in single disease trials. Thus, we will need to thoroughly provide all research personnel with information related to the mechanism of CSA, the consequences of maintaining a hypoxic state and activated sympathetic nervous system in the context of heart failure, the negative relationship between heart failure with untreated SDB and mortality and hospital readmissions, and the importance of a simultaneous treatment approach. We know that if research personnel understand the physiology and scientific basis for the trial, their knowledge may translate into more confidence in describing the objectives of trial to at-risk patients which will increase the likelihood their message is well-received. Proper education of site research personnel is essential for countering misconceptions with evidence-based facts and statistics. The CCC and DCC will be responsible for designing and implementing training; however, we will encourage site Co-PIs to provide supplemental education to their study coordinators and study nurses on a regular basis.

Drawing from the successes of the OSU Sleep Heart Program, training will encompass the importance of empathy in recruiting at-risk patients. Our philosophy has been to “meet people where they are” by acknowledging the fears and concerns of patients with heart failure, making a genuine effort in understanding their challenges, and exhibiting patience as the majority of patients with heart failure are elderly. The training modules will address common rationales of prospective patients that research personnel may have to confront and ways of handling these situations. We will encourage research personnel that may be arranged on disease-specific teams at each site to share experiences with each other and the broader community of research personnel across sites via posting comments on the study website. The generated discussion should result in the proactive suggestions that will translate into better recruitment and retention of participants in the LOFT-HF trial.

Multi-faceted engagement practices will be stressed in all training initiatives for recruitment and retention. Research personnel will be encouraged to form genuine bonds with prospective patients and enrolled patients. The training will address the relationship between rates of retention of enrolled patients with the formation of good relationships between research personnel and patients. In addition to these primary relationships, the training will be applicable to the broader heart failure and sleep medicine clinician community at each site. It is important to realize that the LOFT-HF trial will not occur in a vacuum; other clinicians must be engaged as they will interface with prospective and enrolled patients, delivering care and

may be a potential source of referrals. Therefore, training in-services for various clinical teams including palliative medicine, patient advocacy groups, and social workers, will be provided at the request of each academic site and recruitment materials will be provided to the clinical community as a buy-in measure to generate awareness and support of the LOFT-HF trial.

Training and recruitment materials will explicitly address the relevance of the LOFT-HF trial in the context of current international clinical practice post SERVE-HF, thereby presenting a compelling argument in favor of the prioritization of LOFT-HF trial in the setting of other overlapping clinical trials. OSU CMO routinely puts this comprehensive approach to community engagement into practice during implementation of multi-site research trials.

Each site also will receive nearly real-time feedback on recruitment activities through the study web portal, which displays recruitment graphs by time and site, and includes actual versus projected numbers. This provides positive feedback, allows each site actual data to examine and use for planning and trouble-shooting, and helps to quickly identify sites (and best practices) that can inform study-wide procedures.

10.3.2. Screening, Approaching, and Consenting

The LOFT-HF protocol will be inclusive of multifaceted recruitment practices such as in-person recruitment from both HF and sleep clinics and during hospitalization for acute HF, as well as mailed SDB screening questionnaires. Study coordinators and nurses will identify patients by daily screening of hospital admission rosters for patients diagnosed with acute HF and patients scheduled for routine follow-up in outpatient HF clinics. In addition, potential research patients will be identified by the Co-PIs, sleep medicine and cardiology providers, as well as referrals from patient advocacy groups and the broader clinical community including social workers, patient care resource managers, and palliative care specialists. Study coordinators and nurses will confirm eligibility thorough review of the medical record, approval of site investigators, and approval from the CCC as needed. After initial eligibility criteria are confirmed, patients will be asked to undergo an in-home sleep study (PSG) to evaluate SDB if needed. Those screened from inpatient settings after admission for decompensated HF and without a previous clinical sleep study within the past 12 months can be screened prior to hospital discharge, when in a stable optimized health, using the research PSG device. All sites will be provided with screening tip cards including inclusion and exclusion criteria and an eligibility flowchart. Notably, patients under the age of 21 are ineligible for the trial and will not be approached. Women of childbearing potential may be approached and will be eligible for the trial once a negative pregnancy test is confirmed. Once Good Clinical Practice (GCP) and protocol training has been completed and research personnel have received study certifications, those with the delegated authority to consent patients for the LOFT-HF trial, primarily study coordinators and nurses, will be responsible for approaching prospective patients and initiating and completing the informed consent process. The consenting coordinators and nurses will be experienced clinical research professionals as determined prior to site activation. Patients will sign an informed consent to authorize participation in the study prior to undergoing the sleep study screening procedure or submission of a clinically obtained sleep study to the SRC. Patients with confirmed diagnosis of CSA, and otherwise eligible, will be eligible to be randomized. Study personnel will record inclusion and exclusion criteria in an eCRF. Before final enrollment, these criteria will be entered and verified into a secure study web portal.

The primary PI will be responsible for the overall conduct of the study. The PI may train and designate person(s) to conduct study-related activities but must retain overall responsibility for the trial. All training and delegation of tasks will be documented.

10.3.3. Recruitment of High-Risk Subgroup

Participants will be recruited from outpatient clinics and inpatient clinical settings. To study a high-risk group we will prioritize recruitment strategies that target patients based on poor prognostic markers, including hospitalization within the prior year and/or an elevated BNP or NTproBNP level, to meet the goal of recruiting at least 30% of the sample with high-risk markers. Moreover, the requirement for CSA alone identifies a population with high event rates. We will not use a run-in design that would select samples with better prognosis. Based on the assumptions detailed in our power calculation, including a 35% screen positive rate by sleep study, we will need to screen a total of 2,450 patients with sleep studies to randomize a total of 858 patients (429 per arm). We will stratify randomization based on the presence of high-risk markers. We will monitor total event rates by recruitment sources and the presence of high-risk markers and adjust recruitment strategies, if needed, to ensure our actual event rates are comparable to the estimated event rates.

10.4. Recruitment Rates, Timelines, and Milestones

10.4.1. Year 1: Start-Up or UG3 Phase

During the third quarter of Year 1, we will attempt to activate 10 clinical sites will be activated. The first enrollments will then occur in the last quarter of Year 1, which is anticipated to be in May 2019. A total of 20 patients will be targeted for randomization during the last quarter of this phase. Before the end of Year 1, an additional 20 sites will be activated to begin enrolment at the beginning of Year 2 (the UH3 Phase), bringing the total number of active sites to 30. Approximately 10 additional sites will be identified to serve as potential replacement sites. During the first quarter of Year 1, we will submit a request for TIN services in site identification and we anticipate to meet our target number of secondary and tertiary sites by fourth quarter of Year 1.

10.4.2. Years 2-5: Completion of Enrolment or the UH3 Phase

Assuming the accrual pattern is constant across time (after a slower ramp up in the first year for site activation) at 0.35 patients per center per month, the following milestones will be reached within 54 months: 25% of target enrollment (n=215) in Jan 2021, 50% of target enrollment (n=429) in Jan 2022 75% of target enrollment (n=644) in Jan 2023, and 100% enrollment (n=858) in January 2024.

10.4.3. Recruitment Rate Contingencies

Based on prior experience and on a survey of proposed investigational sites, the expected rate of randomization is 0.25 patients per center per month. The possible range of assumed randomization rates is 0.25-0.5 patients per center per month (or a screening/consent rate of about 1.5 to 3 patients per center per month). The revised site number is 50 as discussed previously. The decision to open additional sites will be made early based on the monitored monthly accrual target. Given the per patient reimbursement to sites, there is little additional cost to opening new sites. The updated budget and revised site activation process will ensure low cost and burden of adding additional sites. The CCC is committed to cover any cost overruns in site initiation fees (estimated to be \$40,000 or less) via its own contingency funds, if an expansion of sites becomes necessary. Alternatively, the period for patient enrollment and randomization could be extended, within the current budget limits. However, this is a less preferable contingency, as completion of enrollment and randomization on schedule is essential to providing a timely assessment of the central hypothesis of LOFT-HF.

10.5. Recruitment and Retention Monitoring

Successful recruitment and retention are critical for the success of any clinical trial and are often more challenging in operation than anticipated during planning. Extensive experience with strategies for optimizing recruitment and retention, including careful selection of participating sites, ongoing monitoring and real-time feedback, capitating payments, providing patient stipends, and sharing expertise across sites in “what works”, will be utilized. Each clinical center has experience in sleep and CV trials and has direct access to large numbers of patients with HF. Sites have Co-Is with good working relationships and expertise in both sleep medicine and cardiology, promoting multi-disciplinary collaboration. A Recruitment, Retention and Operations Subcommittee (RROS) will be established that will include coordinators from representative clinical sites, the CCC Project Manager, and two site PIs.

The committee will design recruitment brochures, oversee the development of newsletters, and provide input into developing the community-facing web portal. Patient representatives from a sleep apnea patient network will provide input into recruitment materials to ensure patient-centeredness. The importance of recruitment of women and minorities will be stressed during training, and we will work with site personnel to use various recruitment materials in ways that promote recruitment of these populations (i.e. placing materials in women’s health clinics and on community accessible websites affiliated with the site). We have selected sites from across the U.S. and Canada as another strategy for increasing demographic diversity. In addition, the LOFT-HF study will utilize diverse recruitment practices including IRB-approved print and electronic versions of recruitment posters, pamphlets, letters, and other study promotional advertisements that can be disseminated in research and clinical offices and other applicable public spaces and via mail, email, website, patient medical record applications, TV and/or radio.

In addition to patient engagement training, we will offer a participation stipend in order to enhance retention. The study will require four in-person or remote study visits including the initial screening visit in which patients elect to complete an overnight sleep test if needed and three 1-hour in-person or remote visits at baseline, 6 month, and 12 month, as well as multiple phone follow ups. Participants can receive check-in by telephone, email and/or text messaging in order to maximize retention. Text messaging will only be utilized with participants who agree to receive text messages. We will offer a participation stipend.

Patients will receive research participation stipends at various visit milestones: \$50 for each in-person visit or remote data collection visit and \$20 for phone follow-up. The average total stipend of \$340 is justifiable reimbursement to compensate patients and for an average of 15 hours of study time, as well as associated travel times in the region. We anticipate this will increase enrollment without introducing selection bias and will improve retention in the study.

Recruitment and retention statistics will be posted in real-time on a study web site, including graphs that show deviations from projections. Sites that fail to meet projections for 2 consecutive months will be asked to provide a report with an analysis and action plan to the Steering Committee. If continued lags are observed, Drs. [name] and [name], in consultation with the Steering Committee and DSMB/NHLBI, will determine further actions, which may include replacement of the site.

11. Statistics

11.1. Description of Study

LOFT-HF is a Phase 3, multicenter, randomized, double-blind, sham-controlled outcomes trial with parallel group design, with patients randomized to either control (optimal guideline based medical treatment [GDMT] plus sham NOXT) or active treatment (optimal GDMT plus NOXT)

in a 1:1 ratio. The primary objective is to evaluate the long-term effects of NOXT on the mortality and morbidity of patients with stable heart failure with reduced ejection fraction (HFrEF), already receiving optimal GDMT who have central sleep apnea (CSA). The secondary objectives are to evaluate patient-reported outcomes (disease-specific and generic quality of life); disease-specific mortality; and cardiovascular events. Subgroup analyses are planned to identify which patients treated with NOXT benefit most based on physiological endotypic traits. Adults, ages 21 years and older, with HFrEF and CSA who meet study eligibility criteria, will be recruited from approximately 50 well-established cardiovascular medicine/sleep centers, and further evaluated with sleep studies to identify the presence of CSA. It is anticipated, based on the literature and our experience conducting similar screening, that about 35% of participants will be eligible after PSG. Approximately 2,450 patients will be recruited to undergo PSGs to randomize a total of 858 patients (429 per arm). Participants will undergo standardized assessments including anthropometry, blood pressure, and questionnaires at baseline and at 6 and 12 month follow-up in-person or remote visits. Telephone calls will be conducted at months 1, 3, 9, and every 6 months after the 12 month visit until the last participant has completed his 12-month visit. Adverse events, hospitalizations and vital status will be collected over the entire intervention period. Given a 3.5 accrual period, mean follow-up time is estimated at 2.5 years (max 4.5 years).

11.2. Statistical Analysis Approaches

Primary analyses will follow the “intention-to-treat” principle; that is, individuals will be analyzed according to their assigned treatment group, whether or not they receive the study treatment as assigned. Every effort will be made to obtain follow-up data on all randomized subjects, whether or not they follow their assigned treatment. Preliminary Analyses

Our approach will involve close collaboration between clinical experts (on the Steering Committee and Scientific Advisory Committee) and biostatisticians, while ensuring appropriate blinding. Interim analyses of baseline variables (aggregated across intervention groups) will be conducted early in the study to ensure that the collected and derived data follow the assumed distributions, and that appropriate methods for identifying outliers and for computing clinical scores are implemented. Reports will provide a full description of the distributions of each study variable, along with indices of associated data quality, and include graphical displays. The amount and patterns of missing data, if any, will be characterized. Measures that are not normally distributed may be transformed to meet model assumptions. Before conducting final analyses, descriptive statistics will be generated using the total data set, ensuring that outliers or potential discrepancies in the data are resolved.

11.2.1. Descriptive Comparisons between Treatment Groups at Baseline and Over Time

Descriptive analyses will be performed to characterize the treatment groups, and to confirm that the randomization resulted in no important group differences at baseline. Study endpoints, dropout rates, cross-over rates, and patterns of missing data will be described. Graphical methods such as stem-and-leaf diagrams, boxplots, and scatter plots will be used to examine distributions, and guide the choice of transformations.

11.2.2. Statistical Approaches to Testing for Treatment Differences

The primary analysis is in the intention-to-treat population that consists of all patients randomized. The primary study endpoint is the time to first event (all-cause death, HF-related hospitalization, life-saving CV procedure), as assessed by the CEC. The primary analysis will

use a Cox proportional hazard model relating the primary outcome and treatment indicator, adjusting for the stratification factor.

The null hypothesis (H0) is: The distribution of time to first event in the intervention group is identical to that in the control group. The alternative hypothesis (H1) is:

The distribution of time to first event in the intervention group differs from time to first event in the control group.

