2.2. Study Rationale

In the current study, the role of nocturnal oxygen as a physiologically-sound option for treating patients with CSA and HFrEF will be evaluated. The pathogenesis of CSA (and CSR) in HFrEF relates to an increased gain of the respiratory control system to hypoxia and sensitivity to hypocapnia, which together trigger recurrent cycles of hyperventilation and central apneas (21,30). Hypoxia amplifies the controller gain for changes in PaCO₂ and reduces intrapulmonary gas stores of oxygen (causing “under-damping”). Accordingly, use of low flow oxygen can stabilize the breathing pattern by reducing the hyperventilation phase of CSA and the subsequent hypocapnia that leads to apneas. Oxygen supplementation also attenuates the individual’s overall exposure to hypoxia, a known contributor to sympathetic over-activity,

ischemia, pulmonary hypertension, and vascular dysfunction (21,30). The adverse effect of hypoxemia was highlighted in the results of a recent large observational study in patients with HFrEF that reported that overnight hypoxemia predicted mortality more strongly than AHI (31). Specifically, this study demonstrated that it was the time below a saturation of 90%, and not the AHI, that predicted excess mortality in a dose dependent manner. This association between nocturnal hypoxemia as a more potent predictor of mortality than the AHI in HFrEF patients has been observed by others.

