5.4. Randomization

Patients meeting all of the inclusion and none of the exclusion criteria will be randomized to one of two groups, a control group receiving optimal GDMT and sham NOXT and a treatment group receiving optimal GDMT and active NOXT.

Patients will be randomly assigned to one of the two study groups in a 1:1 ratio using a permuted block design, stratified by the presence or absence of high-risk markers (hospitalization for HF in the last 12 months and/or an elevated outpatient BNP or NTproBNP level), within sites. Eligible participants will be randomized via a web-based randomization module, initiated by the research coordinator at the participating clinical center. The data management system will confirm all eligibility criteria, and will deliver a randomization identifier (e.g., A or B). Randomization codes also will be linked to identifiers of each oxygen concentrator, providing the ability to assign a participant a concentrator without unblinding local staff. The randomization distributions and system will be re-assessed on a quarterly basis to ensure that it is working as expected. To minimize problems with connectivity, staff will be asked to confirm Internet connectivity at the beginning of the baseline visit to avoid any problems with entry of the randomization case report form. If problems arise with connectivity during a given baseline visit, site staff will be asked to immediately contact the Data Coordinating Center to resolve these; a manually generated randomization assignment would then be generated based upon the subject stratification factor.

6. Investigational Intervention

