8.4. Detailed Visit Schedule

Screening/Consent

1. Obtain signed written consent
2. Document patient demographics (Health Questionnaire CRF)
3. Perform medical history (Health Questionnaire CRF) and medication review.
Completion of a physical examination is optional. Results of a recently completed physical examination during a clinical encounter may be recorded. The site may perform a physical examination at the discretion of the PI either in-person or via telehealth.

4. Evaluate NYHA classification
5. Document that all of the inclusion criteria (except for the sleep eligibility criteria) and none of the exclusion criteria are met (this defines a potentially eligible study patient)
6. Submit de-identified clinical sleep studies to the SRC or administer in-home PSG (if sleep eligibility criteria are met, this defines an eligible patient)

Baseline Visit (to occur within 2 weeks of final eligibility [sleep eligibility] screening)

1. If interim clinical change, repeat medical history and medication review, and reassess NYHA classification. A physical examination is optional.
2. Administer KCCQ, EQ-5D, PHQ-8, and PROMIS questionnaires
3. Provide standard sleep education
4. Randomize patient (within 48 hours of Baseline Visit)
5. Arrange for immediate delivery of oxygen concentrator, by contracted DME provider or staff, for in-home use

(Note: measures that were not completed during the screening visit and not required to determine eligibility, may be collected at the Baseline Visit.)

1-Month Follow Up Call (\pm 1 week)

1. Assess for study intervention (sham/NOXT) adherence (Phone contact CRF)
2. Assess for AEs (Phone contact CRF)
3. Determine if any medication changes have occurred since last contact (Phone contact CRF)
4. Determine if any clinical outcomes events have occurred since last contact (Phone contact CRF)

3-Month Follow Up Call (\pm 10 days)

1. Assess for study intervention (sham/NOXT) adherence (Phone contact CRF)
2. Assess for AEs (Phone contact CRF)
3. Determine if any medication changes have occurred since last contact (Phone contact CRF)
4. Determine if any clinical outcomes events have occurred since last contact (Phone contact CRF)

6-Month In-Clinic or Remote Follow Up Visit (\pm 2 weeks)

1. Assess for study intervention (sham/NOXT) adherence (Phone contact CRF)
2. Assess for AEs (Phone contact CRF)
3. Determine if any medication changes have occurred since last contact (Phone contact CRF)

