We hypothesize a 20% reduction in the 1-year composite event rate, which is high enough to change practice. This effect is within the range of that observed across intervention studies (ranging from 35% for cardiac resynchronization therapy and beta blockers to 15% to 25% for other medications). We anticipate a 1-year event rate of 40% in the control group based on the HF literature showing that patients with advanced HF will experience annual morbidity and

mortality event rates of approximately 40% or greater, especially in the setting of co- morbid CSA.

A total sample of 858 subjects (429 in each arm) achieves 87.9% power at a 5% significance level to detect a hazard ratio (HR) of 0.755 when the 1-year event rate in the control group is 40%, using a two-sided logrank test. We assume a 5% cross-over throughout the study and 10% loss to follow-up throughout the study, and a Cox model with exponential distribution (assuming constant hazard rate), and a 2.49 average length of follow-up.

Original and Revised LOFT-HF Patient Accrual

	Original*	Revised ^{\$}		
Accrual end date	Jan 31, 2023		Jan 31, 2024	
Additional Follow-up Period	12 months	6 months	9 months	12 months
Average length of follow-up	2.75 years	2.49 years	2.74 years	2.98 years
Power	90.2%	87.9%	89.8%	90.4%

*: Corresponds to calculations provided in the original study protocol. Assumes the accrual pattern is uniform over 3.5 years.

\$: Based on the revised projected accrual pattern allowing a slower accrual during siteactivation.

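### The primary Cox model adjusts only for the high-risk stratification factor; pre-specifying age, NYHA class, LVEF and nocturnal hypoxemia as covariates would be a cheap gain in power, though the planned test is valid as it stands.

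*Combined protocol and SAP*

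**What the plan says.** Section 11.2.2 analyzes all randomized patients by intention to treat, with a Cox model "relating the primary outcome and treatment indicator, adjusting for the stratification factor". Under 5.4, patients are allocated "in a 1:1 ratio using a permuted block design", stratified within sites by one yes/no marker: HF hospitalization in the last 12 months and/or a raised outpatient BNP or NT-proBNP.

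Other baseline information is available before randomization:

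- Age and LVEF are eligibility criteria (5.2.2).
- The screening visit includes "Evaluate NYHA classification" (8.4).
- Every patient needs a sleep study centrally scored by the reading center (8.2), and a research study is repeated if it lacks more than two hours of clean oximetry (8.5).

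Section 2.2 cites a study in which "overnight hypoxemia predicted mortality more strongly than AHI", with a dose-dependent relation to time below 90% saturation, and lists LVEF among the predictors of survival. Section 3.1 plans to use LVEF and hypoxemia as subgroup predictors. Section 11.2.3 allows covariate-adjusted models for secondary endpoints. No covariate-adjusted analysis of the primary endpoint is named.

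On power, 11.2.5 says that the sample "achieves 87.9% power at a 5% significance level to detect a hazard ratio (HR) of 0.755", "using a two-sided logrank test".

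**The concern.** In a Cox model, leaving out covariates that predict the outcome lowers power even when randomization is perfect. Unlike in a linear model, the gain from adjusting does not come from a smaller standard error. The conditional log hazard ratio lies further from zero than the marginal one, while its standard error hardly changes. A trial that already holds prognostic baseline data in every patient and does not use them may therefore give up power that would cost no extra patients or follow-up.

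**Working it through.** **Inputs from the plan** (11.2.5, 11.3): 429 patients per arm; two-sided 5%; one-year event rates of 40% in control and 32% on treatment (a 20% reduction); 10% loss and 5% cross-over over the study; accrual over 4.5 years with a slow start to the end of May 2020, then six months' follow-up; mean follow-up 2.49 years; 520 events.

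**Inputs that are assumptions:** 60 patients in the first 10 months (this gives the stated 2.49 years); a stratification factor with HR 1.5 and 50% prevalence; and the strength of the added covariates. Strength is expressed as the SD of their combined score on the log-hazard scale, over and above the stratum. The documents give no figure for it.

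**Step 1: reproduce the plan.** The hazards are −ln(0.60) = 0.511 and −ln(0.68) = 0.386, and their ratio is 0.755. With exponential dropout and gradual two-way cross-over reaching 10% and 5% at year 5, 522 events are expected and the average HR is 0.7597. Power is Φ(½√522 × |ln 0.7597| − 1.96) = Φ(3.14 − 1.96) = 88.1%. The plan states 87.9% and 520 events. Faster dropout or cross-over gives 85.9% to 87.4%. The stated figure therefore reproduces, and it assumes no covariate adjustment.

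**Step 2: add covariates.** Cox fits were simulated with 4,000 trials per row (Monte Carlo error about 0.6 points), with dropout but no cross-over, and with the conditional HR chosen so that one-year rates stay at 40% and 32%.

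| Residual SD (HR per SD) | Stratum only: HR (SE), power | Plus covariates: HR (SE), power | Gain, points |
|---|---|---|---|
| 0.2 (1.22) | 0.753 (0.0898), 88.6% | 0.750 (0.0899), 89.4% | 0.8 |
| 0.3 (1.35) | 0.758 (0.0901), 86.6% | 0.750 (0.0902), 89.3% | 2.7 |
| 0.5 (1.65) | 0.764 (0.0909), 84.5% | 0.742 (0.0912), 90.8% | 6.3 |
| 0.7 (2.01) | 0.766 (0.0922), 82.5% | 0.727 (0.0925), 92.8% | 10.3 |

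The SD 0.5 row can be checked by hand. Stratum only: |ln 0.764|/0.0909 = 2.96, and Φ(2.96 − 1.96) is about 84%. Adjusted: |ln 0.742|/0.0912 = 3.27, and Φ(3.27 − 1.96) is about 90.5%.

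**Step 3: covariates that predict nothing.** A separate simulation fitted four covariates individually, so that the cost of estimating them is included (2,500 trials, conditional HR 0.755, no cross-over). With no prognostic value, power was 88.5% stratum-only and 88.3% adjusted, a difference within simulation error. Type I error with adjustment was 4.9% to 5.5%.

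**The case against.** The case for leaving the model alone has weight:

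- **The stratum already carries prognosis.** Section 4.1 treats recent HF hospitalization and raised natriuretic peptide as markers of poor prognosis. They probably share information with NYHA class and LVEF. This stands, and it is why the SDs above are residual to the stratum.
- **Strong covariates are not shown.** Section 2.2 ties hypoxemia and LVEF to mortality or survival, without effect sizes and not to the composite. Neither NYHA class nor age is named as an independent predictor, and LVEF is restricted to 50% or less. This also stands, so the lower rows of the table cannot be presumed.
- **The data are uneven.** LVEF may come from four modalities, dated within a year in the synopsis but with no window in 5.2.2, and it has no row in the visit table (8.8). Oximetry comes from clinical, home and in-hospital studies. These points call for a few lines of specification and do not argue against adjustment.
- **A fuller analysis plan may exist.** Section 11.2.4 refers to one for effect modifiers, so absence can be stated only for the text available.

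A reader might also draw three stronger conclusions that the documents do not support:

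- **That the planned hazard ratio is biased or the test flawed.** The difference between marginal and conditional hazard ratios is non-collapsibility. The null in 11.2.2 is equality of the two event-time distributions, and the planned test is valid for it.
- **That the missing covariates explain the fall in stated power from 90.2% to 87.9%.** The table in 11.2.5 attaches that change to the revised accrual with six months of additional follow-up.
- **That real power may be 80% or 73%.** Those figures arise at SDs of 0.5 and 0.7 if 0.755 is treated as the conditional HR. The plan derives 0.755 from one-year rates of 40% and 32%, which makes it a marginal quantity.

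**Conclusion.** The point holds as an efficiency improvement. The primary model is valid, its power statement reproduces, and nothing in 11.2.2 needs correcting as an error. Adjustment would add about 1 point of power if the covariates are weak (SD 0.2), about 3 at SD 0.3 and about 6 at SD 0.5. For scale, the table in 11.2.5 shows that extending additional follow-up from 6 to 12 months buys 90.4% − 87.9% = 2.5 points.

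The size rests on assumed SDs, an assumed stratum effect and no cross-over in the simulation, so the gain is better supported than the absolute power levels. The direction is firmer: power rose in every setting with prognostic covariates and was essentially unchanged without them.

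**What to change.** Before unblinding, amend 11.2.2 as follows:

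- Make the primary model a Cox model with treatment, the stratification factor, age, NYHA class (II vs III/IV), LVEF (continuous) and percent time below 90% saturation.
- Name a transformation for the saturation variable. The small study in 2.2 reports 23 ± 21% before oxygen, which points to marked skew in a quantity that cannot fall below zero.
- Give a simple rule for missing baseline values, applied without reference to arm (for example, imputing the overall mean), so that every randomized patient stays in the analysis. Confirm that the numeric LVEF is recorded, not only that the threshold was met.
- State that the interim boundaries in 11.2.5 use the same model.
- Report the stratum-only hazard ratio as a sensitivity analysis.
- State whether site, within which randomization is stratified (5.4, 8.2), belongs to the stratification factor in the model.

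BNP or NT-proBNP should not be added as a further covariate, because the visit schedule does not collect it in everyone. The cost is wording in the plan plus one check of the database. The small downside is that the primary hazard ratio becomes conditional on these covariates and is not directly comparable with the planned 0.755; the stratum-only result keeps that comparison available.
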